ADAS-Cog ₁₃	X			X			X			X				See footnote a.
ADCS-ADL	X			X			X			X				See footnote a.
CDR	X			X			X			X				See footnote a.
MMSE	X			X			X			X				See footnote a.
DSST medicines version	X			X			X			X				Collect via eCOA only when available.
Safety Assessments														
C-SSRS since last visit	X	X	X	X	X	X	X	X	X	X	X	X	X	If visit is not conducted on site, may collect by phone.
Self-Harm Supplement Form	X	X	X	X	X	X	X	X	X	X	X	X	X	If visit is not conducted on site, may collect by phone.
Self-Harm Follow-up Form	X	X	X	X	X	X	X	X	X	X	X	X	X	Required if triggered by Self-Harm Supplement Form per instructions. If visit is not conducted on site, may collect by phone.
Laboratory Tests and Sample Collections^c														
Hematology	X			X			X			X				
Clinical Chemistry and eGFR (CKD-EPI)	X			X			X			X				eGFR calculated by Lilly-designated lab.
Urinalysis and Urinary protein/creatinine ratio (UPCR)	X						X							UPCR calculated by Lilly-designated lab.

Visit No.:	V2	V3	V4	V5	V6	V7	V8	V9	V10	V11	V12	V13	V14	Notes
Week Relative to Randomization	0	4	8	12	16	20	24	28	32	36	40	44	48	Procedures for some visits may take more than 1 day.
Tolerance Interval for Visit (Days)	0	-7 to +10	±7	±7	±7	±7	±7	±7	±7	±7	±7	±7	±7	
PK Samples (Predose)		X	X	X	X		X			X				Do not collect if the last IP infusion was >6 months prior to the scheduled visit. Predose collections may be collected from the IV site prior to the infusion.
PK Samples (Postdose)	X			X			X							Do not collect if the last IP infusion was >6 months prior to the scheduled visit. Collect within 30 minutes of IP infusion completion. Collect from the arm that IP was not administered through.
Immunogenicity (ADA) Samples	X	X	X	X	X		X			X				
NfL/GFAP	X			X			X			X				
P-tau	X			X			X			X				
Aβ	X			X			X			X				
Exploratory Biomarker Samples	X			X			X			X				Collect unless not allowed or unfeasible due to local regulations.
Other Safety Measures														
Weight	X			X			X			X				
Vital signs and temperature	X	X	X	X	X	X	X	X	X	X	X	X	X	Sitting BP, pulse, and temperature will be measured at all visits. In addition, orthostatic BP and pulse will be measured at V2, V5, V8, V11, and unscheduled visits.
ECG	X						X							Perform prior to administration of IP. Unscheduled ECGs may be performed at the discretion of investigator.

Visit No.:	V2	V3	V4	V5	V6	V7	V8	V9	V10	V11	V12	V13	V14	Notes
Week Relative to Randomization	0	4	8	12	16	20	24	28	32	36	40	44	48	Procedures for some visits may take more than 1 day.

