Tolerance Interval for Visit (Days)	0	-7 to +10	±7	±7	±7	±7	±7	±7	±7	±7	±7	±7	±7	
MRI		X		X			X							Perform at least 1 day prior to or after cognitive and functional tests, if applicable. MRI at V3 is to be performed and reviewed prior to V3 infusion and may occur no sooner than 21 days after the first infusion. If infusions are suspended after the first, second, or third dose, an MRI is to be performed and reviewed prior to the fourth infusion. MRI at V5 is to be performed and reviewed prior to V5 infusion. MRI at V5 may occur up to 14 days before the scheduled visit window without protocol deviation. Unscheduled MRIs may be performed at the discretion of investigator, for example if titration is delayed due to temporary suspension of infusions.
Additional Efficacy Measures														
Florbetapir F18 PET scan							X							

Visits 15 through 21 and EDa

Visits without cognitive and functional scales are eligible to be conducted remotely, via mobile healthcare coordinated with and approved by the sponsor, if permitted by local regulations.

Visit No.:	15	16	17	18	19	20	21	EDa	Notes
End of Week Relative to Study Medication Start	52	56	60	64	68	72	76		If a participant discontinues before V21, perform EDa assessments, then the follow-up visits 12 weeks after the last dose received.
Tolerance Interval for Visit (Days)	±7	±7	±7	±7	±7	±7	±7		
Contact IWRS – register visit	X	X	X	X	X	X	X	X	For all visits.
Contact IWRS – dispensation of IP	X	X	X	X	X	X			For visits where IP will be dispensed.
Physical/neurological examination	X			X			X	X	V18 is a brief physical and neurological exam, as described in Section 8.2.1. Any clinically significant changes from baseline on physical/neurological examinations should be noted on the AE CRF.
Previous/concomitant medications	X	X	X	X	X	X	X	X	
Preexisting conditions/adverse events	X	X	X	X	X	X	X	X	
IP administered	X	X	X	X	X	X			Administered by IV infusion. The participant should be observed for a minimum of 60 minutes following the end of each infusion.
Efficacy Measures									
ADAS-Cog ₁₃	X			X			X	X	See footnote a.
ADCS-ADL	X			X			X	X	See footnote a.
CDR	X			X			X	X	See footnote a.
MMSE	X			X			X	X	See footnote a.
DSST medicines version	X			X			X	X	Collect via eCOA only when available.
Safety Assessment									
C-SSRS since last visit	X	X	X	X	X	X	X	X	If visit is not conducted on site, may collect by phone.

Visit No.:	15	16	17	18	19	20	21	EDa	Notes

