RUD-Lite	X						X							Collect RUD-Lite at W78 only if not collected at W76 via AACI Addendum 4. See footnote e.
QOL-AD	X						X							Collect QOL-AD at W78 only if not collected at W76 via AACI Addendum 4. See footnote e.
Safety Assessments														
C-SSRS since last assessment				X			X			X				
Laboratory Tests and Sample Collections														
Hematology				X			X							
Clinical chemistry and eGFR (CKD-EPI)				X			X							eGFR calculated by Lilly-designated lab.
PK Samples (Predose)				X			X							Do not collect if the last IP infusion was >6 months prior to the scheduled visit. Predose collections may be collected from the IV site prior to the infusion.
Immunogenicity (ADA) Samples				X			X							
NfL/GFAP				X			X			X				
P-tau				X			X			X				
Aβ				X			X			X				
Exploratory Biomarker Samples				X			X			X				Collect unless not allowed or unfeasible due to local regulations.
Other Safety Measures														
Weight				X			X			X				

Visit No.:	V22	V23	V24	V25	V26	V27	V28	V29	V30	V31	V32	V33	V34	Notes
Week Relative to Randomization	78	82	86	90	94	98	102	106	110	114	118	122	126	Procedures for some visits may take more than 1 day.
Tolerance Interval for Visit (Days)	±7	-7 to +10	±7	±7	±7	±7	±7	±7	±7	±7	±7	±7	±7	
Vital signs and temperature	X	X	X	X	X	X	X	X	X	X	X	X	X	Sitting BP, pulse, and temperature will be measured at all visits. In addition, orthostatic BP and pulse will be measured at V22, V25, V28, V31, and unscheduled visits.
MRI		X		X			X							Perform at least 1 day prior to or after cognitive and functional tests, if applicable. MRI at V23 is to be performed and reviewed prior to V23 infusion and may occur no sooner than 21 days after the V22 infusion. If infusions are suspended after the first, second, or third dose of the extension period, an MRI is to be performed and reviewed prior to the fourth infusion. MRI at V25 is to be performed and reviewed prior to V25 infusion. MRI at V25 may occur up to 14 days before the scheduled visit window without protocol deviation. Unscheduled MRIs may be performed at the discretion of investigator, for example if titration is delayed due to temporary suspension of infusions.
Additional Efficacy Measures														
Florbetapir F18 PET scan							X							

Visits 35 through 41, EDb, and follow-up

Visits without cognitive and functional scales are eligible to be conducted remotely, via mobile healthcare coordinated with and approved by the sponsor, if permitted by local regulations.

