8.3.7. Amyloid-Related Imaging Abnormalities (ARIA-E and ARIA-H)

While most cases of ARIA are asymptomatic, serious cases have been reported. Available data suggests serious cases are most likely to occur early in dosing, after the first, second, or third infusion.

When symptoms are present in association with these imaging abnormalities, they have been reported to include, but may not be limited to, headache, vomiting, unsteadiness, dizziness, tremor, confusion, visual disturbances, speech disturbances, worsening cognitive function, alteration of consciousness, and seizures (Ostrowitzki et al. 2012; Sperling et al. 2012; VandeVrede et al. 2020; Mintun et al. 2021; Swanson et al. 2021).

If a participant simultaneously develops more than 1 of the symptoms suggestive of ARIA-E, then an unscheduled MRI should be performed. A single symptom suggestive of ARIA-E of sufficient severity may also warrant a MRI.

If the above-mentioned symptoms are reported, and:

- ARIA-E is suspected, then the abnormality is best detected by FLAIR sequences on MRI, while
- ARIA-H is best detected with the T2* gradient-recalled echo on MRI.

An unscheduled MRI with these imaging sequences should be obtained upon suspicion of ARIA. If ARIA is present, it is recommended to repeat MRIs with these sequences every 4 to 6 weeks until resolution of ARIA-E or stabilization of ARIA-H is documented. For asymptomatic or mild symptoms, the participant can be observed; for moderate symptoms associated with ARIA-E, the use of oral or IV steroids can be considered. In the case of severe symptoms associated with ARIA-E, it is recommended to hospitalize the participant for close observation and consider the use of IV steroids such as high-dose dexamethasone or a similar agent (see Manual of Operations for more detail).

The unscheduled MRI should be performed in the same manner as the currently scheduled MRIs in the protocol, which includes sending the images for central review (Section 8.2.5).

For procedure to follow in the event of ARIA-E or ARIA-H, see Section 7.1.1.1.

In the event of a finding of ARIA-E on MRI, the investigator is to complete the ARIA-E Related Events CRF regarding the presence or absence of symptoms related to the ARIA-E, and ARIA-E should be reported as an adverse event in the Adverse Events CRF.

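### The early allowance for the V5 and V25 MRI is not anchored to the third infusion, so a scan 7 days after an on-target third dose complies (at the extreme, one on the same day)

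*Protocol*

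**What the plan says.** All of the timing rules stand in the MRI rows of Protocol Section 1.3.

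- **V3.** The scan is reviewed before the second infusion and "may occur no sooner than 21 days after the first infusion". The V23 note sets the same 21-day floor after the V22 infusion.
- **V5.** "MRI at V5 is to be performed and reviewed prior to V5 infusion". The same note then says "MRI at V5 may occur up to 14 days before the scheduled visit window without protocol deviation".
- **V25.** The extension note is built the same way: "MRI at V25 may occur up to 14 days before the scheduled visit window without protocol deviation".
- **Suspended dosing.** "If infusions are suspended after the first, second, or third dose, an MRI is to be performed and reviewed prior to the fourth infusion". This sets no interval after the third dose either.

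Three other sections give the V5 scan its weight. Section 4.1 puts the first three doses at 700 mg and later doses at 1400 mg, so V5 is the scheduled step. Section 6.6 lists the investigator's dosing options when ARIA develops before the fourth infusion, in the double-blind or the extension period. Section 8.3.7 says that most ARIA is asymptomatic, and of serious cases: "Available data suggests serious cases are most likely to occur early in dosing, after the first, second, or third infusion".

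**The concern.** Two scans are required before an infusion during titration, and the protocol times them differently. The V3 and V23 scans are tied to the infusion before them. The V5 and V25 scans are tied only to the calendar window of their own visit, and that window is then extended 14 days earlier. Nothing ties them to the third infusion, which has its own window of ±7 days.

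At stake is what the last scheduled scan before the step to 1400 mg can show. Taken early, it informs on doses 1 and 2 but may carry little or no information on dose 3. ARIA without symptoms that arises after dose 3 could then reach the fourth infusion undetected. The Section 6.6 options that depend on finding ARIA before that infusion would not come into play. It could also be recorded at a later time point than the one at which it arose.

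**Working it through.** **Inputs** (Section 1.3 unless stated; Day 0 = randomization, visit day = 7 × week)

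- V2 = Day 0, tolerance 0.
- V3 = Week 4 = Day 28, -7 to +10, so Days 21 to 38.
- V4 (third infusion) = Week 8 = Day 56 ±7, so Days 49 to 63.
- V5 (fourth infusion) = Week 12 = Day 84 ±7, so Days 77 to 91.
- V22 = Week 78 = Day 546 ±7, so Days 539 to 553.
- V23 = Week 82 = Day 574, -7 to +10, so Days 567 to 584.
- V24 = Week 86 = Day 602 ±7, so Days 595 to 609.
- V25 = Week 90 = Day 630 ±7, so Days 623 to 637.
- Minimum dosing interval: 21 days (Section 6.1).

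The protocol prints no day number for the earliest V5 or V25 MRI, so there is no stated figure to reproduce.

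**Step 1: earliest compliant MRI** = opening of the visit window - 14.

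- V5: 77 - 14 = Day 63.
- V25: 623 - 14 = Day 609.

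Each is the last in-window day for the third infusion of that period.

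**Step 2: gap from the third infusion to the earliest MRI**

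| Third infusion | V4 day | Gap to Day 63 | V24 day | Gap to Day 609 |
|---|---|---|---|---|
| First day of window | 49 | 14 days | 595 | 14 days |
| On target | 56 | 7 days | 602 | 7 days |
| Last day of window | 63 | 0 days | 609 | 0 days |

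The MRI row's 1-day separation applies to cognitive and functional tests, and none are scheduled at V4 or V24. It does not exclude the 0-day case, and nothing requires a scan on that day to follow the infusion.

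**Step 3: how much of the allowance is affected.** With an on-target third infusion, 21 days are reached on Day 56 + 21 = Day 77, when the V5 window opens. Every day of the early allowance (Days 63 to 76) therefore gives a gap of 7 to 20 days. The 21 days serve here only as the protocol's own comparator from V3 and V23.

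**Step 4: a late V3.** If V3 falls on Day 38, the dosing-interval rule puts V4 no earlier than 38 + 21 = Day 59. An in-window V4 is then Days 59 to 63, and the earliest MRI is 63 - 59 = 4 down to 63 - 63 = 0 days after dose 3.

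**Step 5: age of the scan at the fourth infusion.** A Day 63 scan is 84 - 63 = 21 days old at an on-target V5 and 91 - 63 = 28 days old at the end of the window.

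**Step 6: next scheduled MRI.** After V5 it is V8 (Week 24), following the V5, V6 and V7 infusions. After V25 it is V28 (Week 102), following the V25, V26 and V27 infusions.

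**Sensitivity.** If the allowance were counted from the visit date instead of the window, the earliest V5 MRI would be 84 - 14 = Day 70, with gaps of 21, 14 and 7 days. The same-day overlap would go, but an on-target or late third infusion would still leave less than 21 days. The current text says window.

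**The case against.** **The V3 floor may not be a dose anchor at all.** V2 has no tolerance and the V3 window opens on Day 21, so the 21-day floor coincides with that window and with the minimum dosing interval. For V3 this is mostly right. It fails for V23. V22 floats by ±7 days, and if it falls on Day 553 the floor gives 553 + 21 = Day 574, a week after the V23 window opens on Day 567. There the floor does work that the calendar does not, and V5 and V25 have no counterpart.

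**The notes do not contradict each other.** A reader might infer that they do. They do not: each can be followed as written, and no sentence says that the V5 scan exists only to check dose 3. What stands is an unanchored allowance that sits poorly with Sections 6.6 and 8.3.7.

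**The allowance is permissive and buys flexibility** for a scan that must be both performed and reviewed before dosing. That is a legitimate reason. But the note also removes deviation status, so deviation monitoring would not show how often the early days are used.

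**Other safeguards exist.** Section 1.3 and Section 8.2.5 allow unscheduled MRIs at the investigator's discretion. Section 8.3.7 calls for one on suspicion of ARIA. A physical and neurological examination takes place at V5 (a brief one at V25), and adverse events are reviewed at every visit. These stand as partial mitigation, because discretion and symptoms are weak triggers when most ARIA is asymptomatic.

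**A reader might also infer that ARIA from dose 3 will go unseen, or that the same-day scan is the typical case.** The documents support neither. The same-day case needs the last day of one window and the first day of the allowance, and the Section 8.3.7 sentence on timing concerns serious cases rather than all ARIA.

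**Conclusion.** The point holds as a gap in how the early allowance is fixed. On the current wording, a compliant V5 or V25 MRI can fall 7 days after an on-target third infusion, and between 14 and 0 days across that infusion's window. The V3 and V23 notes require at least 21 days after the infusion before them. Asymptomatic ARIA after the third dose could therefore be missed by the scheduled scan until V8, or V28 in the extension.

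The calendar result is certain. The size of the consequence is not: the protocol does not say how often sites scan early, and gives no rate of ARIA between the third and fourth infusions. The conclusion also assumes that the Manual of Operations, which the ARIA sections cite and which was not available, sets no interval for this scan.

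At V25 the point concerns former placebo participants, who repeat the titration, and participants who stayed on 700 mg and may escalate at V25 or after (Section 4.1.3). Others have no scheduled step there. The early scan is not uninformative, since it still covers doses 1 and 2. The matter should be corrected, but it does not undermine the trial's conclusions.

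**What to change.** The sponsor should reconcile the early-MRI allowance in the V5 and V25 notes of Section 1.3 with four things: the V4 and V24 infusion windows, the V3 and V23 notes, the Section 6.6 options for ARIA before the fourth infusion, and the Section 8.3.7 statement on when serious ARIA occurs. The timing is a clinical decision for the sponsor, and no interval is proposed here.

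The change is one of wording in two schedule notes. No extra scan is needed. The cost is slightly less freedom in scheduling the V5 and V25 MRI.

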2.1. Study Rationale

Donanemab is an antibody directed at the pyroglutamate modification of the third amino acid of amyloid beta (N3pG A β) epitope that is present only in brain amyloid plaques. It is being studied for the treatment of Alzheimer's disease (AD). The mechanism of action of donanemab antibody is to target and remove deposited amyloid plaque, a key pathological hallmark of AD, via microglial-mediated clearance. The clinical strategy for donanemab identifies early symptomatic AD patients with existing brain amyloid load, as measured using the amyloid plaque biomarker florbetapir F18 positron emission tomography (PET) imaging in conjunction with the presence of tau pathology in the brain. This strategy is based on the amyloid hypothesis of AD, which postulates that the production and deposition of A β is an early and necessary event in the pathogenesis of AD (Selkoe 2000). Clinical data supporting this hypothesis comes from the observation that parenchymal A β levels are elevated prior to the manifestation of AD symptoms, and further supported by genetic variants of AD that overproduce brain A β and genetic variants that protect against A β production (Jonsson et al. 2012; Fleisher et al. 2015). Furthermore, early in the disease, the presence of brain amyloid appears to increase the risk of conversion from mild cognitive impairment (MCI) to AD dementia (Doraiswamy et al. 2012). These data suggest that removal of deposited amyloid and clearance of A β can result in the slowing of AD progression.

Study I5T-MC-AACI (AACI) is a Phase 3, double-blind, placebo-controlled study to evaluate the safety and efficacy of N3pG antibody (donanemab) in Participants with early symptomatic AD (prodromal AD and mild dementia due to AD) with the presence of brain tau pathology. Study AACI will assess whether removal of existing amyloid plaque can slow the progression of the disease as assessed by clinical outcomes for cognition and function, and by imaging biomarker measures of disease pathology and neurodegeneration over 76 weeks of double-blind observation.

Study AACI expands the Participant population compared to the prior Phase 2 study by including participants with high tau pathology. The primary analysis will test low-medium (intermediate) tau pathology population and the overall population.

2.2. Background

Alzheimer's disease is an age-related neurodegenerative disorder characterized by progressive decline in cognitive function and the ability to perform activities of daily living. The amyloid hypothesis of AD postulates that the accumulation of A β is an early and necessary event in the pathogenesis of AD. This hypothesis suggests that interventions that slow the accumulation of A β plaque in the brain or increase clearance of A β may be able to slow the progression of the AD clinical syndrome. Another hallmark neuropathological lesion of AD is comprised of intraneuronal, neurofibrillary tangles consisting of tau proteins, which spread through the brain and mark disease progression (Braak and Braak 1996). The relationship between these 2 pathologies is still unclear, although the presence of both is necessary for the diagnosis of definite AD.

Converging evidence from both genetic at-risk and age at-risk cohorts suggests that the pathophysiological process of AD begins well more than a decade before the clinical stage now recognized as AD dementia, and that neurodegeneration is already apparent on magnetic resonance imaging (MRI) by the stage of MCI. Like many disorders, AD occurs on a continuum from asymptomatic (preclinical) to MCI, and then to dementia in mild, moderate, and severe stages. Recent clinical trial results in mild-to-moderate AD dementia, as well as evidence from transgenic animal experiments, suggest that treating AD during the earlier stages could have the greatest potential benefit on the disease and inhibiting progression, particularly when considering therapies targeted at A β reduction (Doody et al. 2014; Fleisher et al. 2015; Siemers et al. 2016).

2.2.1. Donanemab Nonclinical Studies

The safety of donanemab, a plaque-specific monoclonal antibody, was assessed in a 6-week toxicity study in cynomolgus monkeys, including evaluations of safety pharmacology and toxicokinetics. The administration of donanemab in monkeys of up to a maximum dose of 100 mg/kg/week (bolus intravenous [IV]) for 6 weeks resulted in no drug-related findings. Repeat-dose hazard identification studies of up to 6 months' duration were conducted in the aged PDAPP (APPV717F) transgenic mouse model of A β deposition to investigate potential effects related to clearance of A β from the brain. In addition, a specialized 3-month study to investigate the potential for cerebral amyloid angiopathy-associated microhemorrhages was conducted in aged PDAPP transgenic mice. These studies in the PDAPP mouse were conducted with mE8c (LSN3026818), a murine analog antibody of donanemab, to avoid limitations due to potential immunogenicity from repeated administration of the humanized antibody to the mouse.

No drug-related findings occurred in the hazard identification studies in PDAPP mice at mE8c doses of up to 100 mg/kg/week (the highest dose tested). Treatment of PDAPP mice with mE8c at 12.5 mg/kg/week for 3 months did not exacerbate cerebral amyloid angiopathy-associated microhemorrhages at a dose that produced a maximum pharmacological response (reduction in deposited brain A β) in these animals.

See the Investigator's Brochure (IB) for additional details regarding nonclinical donanemab studies.

2.2.2. Donanemab Clinical Studies

Two Phase 1 studies (Study I5T-MC-AACC [AACC] and Study I5T-MC-AACD [AACD]) have been conducted in participants with MCI and mild-to-moderate AD. In both studies, rapid and sustained reduction in cerebral amyloid plaques were observed with donanemab doses ≥ 10 mg/kg.

One Phase 2 study (Study I5T-MC-AACG [AACG]) has been conducted in participants with early symptomatic AD and intermediate (low to medium) cerebral tau burden. Treatment with donanemab compared with placebo resulted in a significant slowing of disease progression, as measured by the integrated Alzheimer's Disease Rating Scale (iADRS; Wessels et al. 2015) as well as deep and rapid reduction in amyloid plaque level. Safety findings observed in clinical development include ARIAs, IRRs, and the presence of ADAs (Mintun et al. 2021).

See the IB for detailed safety and PK information regarding donanemab.

